10.2 Tolerability Assessments

Tolerability assessments will be performed by subjects at the surgical site at baseline (pre- and post-procedure), day 7/14, and day 28. Subjects will grade the degree of irritation parameters that they experience based on a 4-point analog scale, described in the table below (with half-point scores used as necessary to better describe the clinical condition):

Parameters	Score 0	Score 1	Score 2	Score 3
Burning	None	Mild	Moderate	Severe
Itching	None	Mild	Moderate	Severe
Pain	None	Mild	Moderate	Severe

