
Procedure
	
 - Subjects will report to the site as screening visit, will be given an informed consent form, HIPAA form, photography release form, Code of Conduct form, and medical history form to complete. - Subjects will be screened on the basis of the selection criteria for study qualification. At day 0, investigator assessment (erythema, edema, scabbing/crusting, and overall wound appearance) and subjective tolerability assessment (burning, itching, pain) will be performed based on 0-4 analog scale. - Subjects will undergo the assigned surgical procedure. - After procedure, photography of the surgical site, investigator assessment and subjective tolerability will be performed, and investigator or staff will apply Healing Ointment immediately followed by a standard bandage. - Subjects will be instructed to apply the provided Healing Ointment to the wound at least twice daily and reapply as needed. - Subjects to return to the site at day 7 (\pm 2 days for head/neck group) or day 14 (\pm 2 days for body group), and day 28 post-treatment (\pm 3 days) for follow-ups. - For each follow-up visit, investigator will perform objective assessment and photography. Subjects will perform additional subjective tolerability assessment and self-assessment questionnaire.

Statistical analysis
	
Clinical grading and questionnaire.

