7.6 Treatments Compliance

Subjects will complete a daily diary, recording treatment product applications and comment during the study. Treatment product and diaries will be dispensed to subjects at Day 0 and reviewed for compliance at Day 28 visit. Treatment product will be visually inspected and weighed prior to distribution at Day 0 and at Day 28. Subjects will be instructed to return the treatment product and daily diary at Day 28 visit. If subjects do not return their treatment product or diary at the end of the study, a verbal confirmation will be obtained for usage compliance, and it will be documented as a note to file.

Any suspected noncompliance with the treatment product or study instructions will be addressed by the Investigator or clinic staff. The Investigator will determine whether a subject's noncompliance will affect the study outcome and whether the data should be excluded from statistical analyses.

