9. STUDY PROCEDURES

The table below represents a summary of the study procedures and evaluation schedule:

1. Visit 1 – Screening
2. Visit 2 – Baseline/Day 0 (surgical procedure)
3. Visit 3 – Day 7 (for head/neck group) or Day 14 (for body group)
4. Visit 4 – Day 28

Test design / flow chart	Visit 1	Visit 2		Visit 3	Visit 4
	Screening	Baseline Day 0 Pre-procedure	Baseline Day 0 Post-procedure	Day 7 or Day 14	Day 28
ICF and qualification/enrollment	X				
Photo consent	X				
Demographics/Med History	X				
Concomitant Meds.	X				
Inclusion and exclusion criteria	X				
CRF		X	X	X	X
Investigator grading		X	X	X	X
Subjective tolerability grading		X	X	X	X
Standardized photography		X	X	X	X
Self-assessment questionnaire				X	X
AE reporting			X	X	X
Treatment product		W	D	W	C/W
Daily diaries			D	C/D	C

For treatment product and/or daily diaries: W = Weigh, D = Distribute, C = Collect

Protocol Version 1:

This document contains confidential, proprietary information.

Protocol GLI.04.US.SL.017

CONFIDENTIAL

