9.1.2. Visit 2 (Baseline/Day 0 – Surgical procedure)

1. Investigator or clinic staff will ask the subjects if they have experienced any changes in their health since the previous visit.
2. Before the surgical procedure, the assessments below will be completed:
 - a. Clinical grading by Investigator as described in section 10.1
 - b. Tolerability assessment by the subjects as described in section.
3. The surgical area will be assessed and prepped for the procedures, followed by procedure execution by Investigator.
4. After the surgical procedure, the assessments below will be completed:
 - a. Standardized photography as described in section 10.3
 - b. Clinical grading by Investigator as described in section 10.1
 - c. Tolerability assessment by the subjects as described in section 10.2
5. Investigator or clinic staff will apply the treatment product to the surgical site followed by standard bandage.
6. Subjects will be given the treatment product with instruction of application, a diary to record usage of the treatment product, and when to contact the Investigator in case of emerging AEs.
7. Subjects will be scheduled for a follow-up visit at Day 7 or 14 (± 2 days) and dismissed from the Clinic.

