11. STATISTICAL ANALYSIS

A descriptive statistical summary will be provided for clinical grading and tolerability assessments. The descriptive summary will be performed for each parameter, including N, mean, median, standard deviations, minimum, and maximum of values at all applicable time points.

Mean of the change from baseline (pre-procedure) will be estimated at applicable post-baseline time point. The null hypothesis, that the mean change from baseline (pre-procedure) is zero, will be tested using methods described in the Statistical Analysis Plan table.

The following will be calculated and reported for each evaluation parameter at applicable post-baseline (pre-procedure) time point:

$$\text{Percent mean change from baseline} = \frac{(\text{postprocedure or visit mean score} - \text{baseline preprocedure mean score})}{\text{baseline preprocedure mean score}} \times 100$$

$$\text{Percent of subjects improved/worsened} = \frac{(\text{number of subjects improved/worsened from baseline preprocedure})}{\text{total number of subjects}} \times 100$$

Questionnaires will be tabulated, and the percentage of all response options (favorable and unfavorable) will be reported for each question and each timepoint.

Statistical Analysis Plan

Evaluation	Change from Baseline Pre-Procedure	Notes/Interpretation
Clinical grading	Paired t-test; If normality fails, a Wilcoxon signed-rank test will be used.	A decrease in scores indicates an improvement
Tolerability assessment	Paired t-test; If normality fails, a Wilcoxon signed-rank test will be used.	A decrease in scores or lack of significant increase indicates tolerability/safety of the treatment product
Self-assessment questionnaire	N/A	Percentage of favorable and unfavorable responses will be provided for each question.

All statistical tests will be 2-sided at significance level alpha = 0.05 unless specified otherwise. *P* values will be reported to 3 decimal places.

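### The Day 0 post-procedure tolerability tests use scores taken before any ointment is applied, and no graded symptom score covers the first 7 (head/neck) or 14 (body) days of use

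*Combined protocol and SAP*

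**What the plan says.** Subjects rate burning, itching and pain from 0 to 3, half points allowed, on four occasions (Section 10.2): "Tolerability assessments will be performed by subjects at the surgical site at baseline (pre- and post-procedure), day 7/14, and day 28".

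Section 9.1.2 fixes the order on Day 0. Step 4 begins "After the surgical procedure, the assessments below will be completed", and its item c is the tolerability rating. Step 5 follows: "Investigator or clinic staff will apply the treatment product to the surgical site followed by standard bandage". The Synopsis has the same order: photography, grading and tolerability come first, and then "investigator or staff will apply Healing Ointment immediately followed by a standard bandage".

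The next rating is at Visit 3: "Subjects will be scheduled for a follow-up visit at Day 7 or 14 (± 2 days) and dismissed from the Clinic". The Section 9 flow chart assigns Day 7 to head/neck and Day 14 to body.

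Section 11 tests whether the mean change from the pre-procedure baseline is zero at each applicable later time point. Its percent-change formula names the post-procedure score alongside the visit scores. For tolerability, the interpretation column says: "A decrease in scores or lack of significant increase indicates tolerability/safety of the treatment product".

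A diary runs alongside (Section 7.6): "Subjects will complete a daily diary, recording treatment product applications and comment during the study". No symptom scale is mentioned for it.

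**The concern.** Two separate problems arise from the same schedule.

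The first is interpretation. A score taken before the ointment reaches the wound cannot describe how the ointment is tolerated. Section 11 draws no distinction between that score and the later ones. If symptoms rise from before to after the procedure, surgery is the reason, yet the rule would count the rise against the product. If they do not rise, the rule would credit an ointment not yet applied.

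The second is coverage. Safety is part of the objective in Section 5.1, but the first graded rating under exposure comes one or two weeks into use. A symptom that starts with early applications and clears before Visit 3 leaves no trace in the scores that Section 11 analyses.

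**Working it through.** The plan states no figure on this point to reproduce. The check is a comparison of schedules plus simple counts.

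**1. Which scores follow exposure**

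| Score | Position relative to first application |
|---|---|
| Day 0 pre-procedure | before (Section 9.1.2, step 2) |
| Day 0 post-procedure | before (step 4c; application is step 5) |
| Visit 3, Day 7 or 14 | after |
| Visit 4, Day 28 | after |

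Two of the four scheduled scores follow any product contact.

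**2. Tests affected.** 3 symptoms × 3 later time points (post-procedure, Visit 3, Day 28) = 9 tests. At post-procedure: 3 × 1 = 3. This assumes one test per symptom and time point with the groups pooled, and that post-procedure counts as an applicable time point, as the formula in Section 11 indicates. Testing by group would double both counts and leave the share at one third.

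**3. Length of the ungraded period.** Visit 3 day ± 2 (Section 9.1.2), as a share of the 28-day study:

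- Head/neck: 7 days (5 to 9); 7/28 = 25% (5/28 = 18% to 9/28 = 32%).
- Body: 14 days (12 to 16); 14/28 = 50% (12/28 = 43% to 16/28 = 57%).

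**4. Applications in that period.** Section 8.3.1 keeps the surgical bandage on for 36-48 hours (1.5 to 2 days), and Section 8.3.2 asks for at least two applications a day. Assuming self-application starts when the bandage comes off, the minimum is 2 × (Visit 3 day − bandage days):

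- Head/neck: 2 × (7 − 2) = 10 to 2 × (7 − 1.5) = 11. Over the window: 2 × (5 − 2) = 6 to 2 × (9 − 1.5) = 15.
- Body: 2 × (14 − 2) = 24 to 2 × (14 − 1.5) = 25. Over the window: 2 × (12 − 2) = 20 to 2 × (16 − 1.5) = 29.

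The clinic application on Day 0 comes on top.

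**5. Other routes for early symptoms**

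| Route | Graded burning, itching or pain? |
|---|---|
| Adverse event collection from consent onward (Section 12.4) | No symptom score; has its own severity classes |
| Diary comment (Section 7.6) | No, free text |
| Irritation item in the Day 7/14 questionnaire (Appendix II) | No, one retrospective agreement rating |

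Where Section 12.1.2 applies (its heading limits it to cosmetic safety studies), a local sign is recorded as a related adverse event only if application stops permanently or corrective treatment is prescribed.

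**6. Illustration, with assumed rates.** The documents give no rate of early irritation. If 5%, 10% or 20% of 20 subjects had a transient symptom, the expected number is 1, 2 or 4. The chance of at least one, 1 − (1 − p)^20, is 64%, 88% or 99%. If all cleared before Visit 3, none would appear in a scheduled score.

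**7. What diary ratings would add.** One rating a day from Day 1 to the day before Visit 3 gives 7 − 1 = 6 ratings per symptom for head/neck and 14 − 1 = 13 for body, where there are now none. With no subject at the threshold, the exact two-sided 95% upper limit, 1 − 0.025^(1/n), is 30.8% for n = 10 and 16.8% for n = 20.

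**The case against.** The schedule is consistent across the Synopsis and Sections 9 and 10.2, so the timing of visits is a design choice and not an error. Nor is the early period unobserved. Adverse events are collected throughout, and at each visit subjects are asked about health problems since the last one (Section 12). They are told on Day 0 when to contact the investigator. The questionnaire's irritation item is tabulated, and a clinically relevant unfavourable answer is reportable as an adverse event whatever its cause. Finally, in a single-arm study, early diary ratings would mix symptoms of the operation with symptoms of the product.

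Much of this stands. A reader might infer that early intolerance is missed altogether. The documents do not support that: intolerance that is reported, leads to stopping or needs treatment has a route into the record. A reader might also infer that scoring begins only once the wound has largely closed, so that the schedule is biased towards a favourable result. The documents give no healing times, so that premise is unsupported. The post-procedure tests could in fact work against the product, because a surgical rise would be read as poor tolerability.

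The objection does not reach two things. None of the other routes yields a graded symptom score for the Section 11 analysis, and none repairs the reading of scores taken before exposure.

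**Conclusion.** The concern holds in two limited forms. First, as Section 11 is written, 3 of the 9 tolerability tests are interpreted as evidence about a product that had not yet been applied. This follows from the order of steps on Day 0 and rests only on post-procedure being a tested time point. Second, graded symptom data are absent for the first 7 days (5-9) in the head/neck group and 14 days (12-16) in the body group. That is at least 10-11 (6-15) or 24-25 (20-29) self-applications, if these start after bandage removal, plus the clinic application. A transient early symptom can be reported, but it cannot enter the graded tolerability analysis. The size and direction of any effect on the trial's conclusion cannot be derived from the documents.

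**What to change.** 1. **Section 11.** Exclude the Day 0 post-procedure comparison from the product-tolerability conclusion. Report it only as a description of the procedure and as the reference before product contact. This is a wording change at no cost.

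2. **Sections 7.6, 10.2 and 11.** Add burning, itching and pain, on the Section 10.2 scale of 0 to 3, to the existing daily diary from Day 0 to Visit 3. For each symptom report each subject's worst score, and n (%) with a score of 2 or more, with an exact 95% confidence interval. State that 1.5 falls below that threshold, since half points are allowed. Report the head/neck and body groups separately, because a maximum over about 7 days is not comparable with one over about 14. Keep these results descriptive, and state that in a single-arm study they cannot separate product from surgical symptoms.

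3. **Diary handling.** Section 7.6 places diary review at Day 28, whereas Section 9.1.3 and the flow chart have the diary collected at Visit 3. Align these so that the early ratings are retrieved at Visit 3.

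The cost is three short ratings a day for one to two weeks, data entry for 20 subjects and one additional table. No extra visit is needed. The diary form is not in the documents, so its layout has to be checked.

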10.3 Standardized Photography

Standardized digital photography of the surgical site will be taken at baseline (pre- and post-procedure), day 7/14, and day 28.

The following guidelines of digital photography are followed:

- Surgical site position is the same in before and after photos
- Same lighting conditions are used and the distance from the camera is same for both before and after photos
- Same room and white background are used for both before and after photos
- Clean skin
- Avoid any object that could interfere with the images such as hair, jewelry, etc.

A total of 4 digital images will be taken of each subject's surgical site using a Canon EOS Rebel T5 digital camera (Canon Inc., Taiwan) under the standard lighting condition.

10.4 Self-Assessment Questionnaire

Subjects will complete self-assessment questionnaire at day 7/14 and day 28. See Appendix II: Self-assessment questionnaire.

Protocol Version 1:

This document contains confidential, proprietary information.

11. STATISTICAL ANALYSIS

A descriptive statistical summary will be provided for clinical grading and tolerability assessments. The descriptive summary will be performed for each parameter, including N, mean, median, standard deviations, minimum, and maximum of values at all applicable time points.

Mean of the change from baseline (pre-procedure) will be estimated at applicable post-baseline time point. The null hypothesis, that the mean change from baseline (pre-procedure) is zero, will be tested using methods described in the Statistical Analysis Plan table.

The following will be calculated and reported for each evaluation parameter at applicable post-baseline (pre-procedure) time point:

$$\text{Percent mean change from baseline} = \frac{(\text{postprocedure or visit mean score} - \text{baseline preprocedure mean score})}{\text{baseline preprocedure mean score}} \times 100$$

$$\text{Percent of subjects improved/worsened} = \frac{(\text{number of subjects improved/worsened from baseline preprocedure})}{\text{total number of subjects}} \times 100$$

Questionnaires will be tabulated, and the percentage of all response options (favorable and unfavorable) will be reported for each question and each timepoint.

Statistical Analysis Plan

Evaluation	Change from Baseline Pre-Procedure	Notes/Interpretation
Clinical grading	Paired t-test; If normality fails, a Wilcoxon signed-rank test will be used.	A decrease in scores indicates an improvement
Tolerability assessment	Paired t-test; If normality fails, a Wilcoxon signed-rank test will be used.	A decrease in scores or lack of significant increase indicates tolerability/safety of the treatment product
Self-assessment questionnaire	N/A	Percentage of favorable and unfavorable responses will be provided for each question.

All statistical tests will be 2-sided at significance level alpha = 0.05 unless specified otherwise. *P* values will be reported to 3 decimal places.

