6. SELECTION AND DISPOSITION OF STUDY POPULATION

6.1 Number of Subjects

A maximum 20 subjects to complete the study, in which 10 subjects with dermatologic procedure on the head/neck and 10 subjects with dermatologic procedure on the body.

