10.1 Clinical Grading by Investigator

Investigator will perform clinical grading at the surgical site on each subject at baseline (pre- and post-procedure), day 7/14, and day 28. Investigator will grade the severity of wound parameters based on a visual analog scale, described in the table below (for erythema, edema, overall wound appearance, half-point scores can be used as necessary to better describe the condition):

Parameters	Score 0	Score 1	Score 2	Score 3
Erythema	None/absent	Mild	Moderate	Severe

Protocol Version 1:

This document contains confidential, proprietary information.

Edema	None/absent	Mild	Moderate	Severe
Overall wound appearance	Excellent (absent of wound)	Good (slightly visible wound)	Fair (moderately visible wound)	Poor (marked visible wound)

Parameters	Score 0	Score 1	Score 2	Score 3	Score 4
Scabbing/crusting	None	Slight (up to 30%)	Moderate (31-60%)	Extensive (61-90%)	Almost complete or complete (91-100%)

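### Section 11 does not say how Visit 3 is reported when it falls on Day 7 for head/neck and Day 14 for body, and it treats a non-significant rise in symptoms as evidence of tolerability

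*Combined protocol and SAP*

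**What the plan says.** Section 6.1 plans at most 20 completers: "10 subjects with dermatologic procedure on the head/neck and 10 subjects with dermatologic procedure on the body". Section 9 places Visit 3 at "Day 7 (for head/neck group) or Day 14 (for body group", and the synopsis and Section 9.1.3 allow ±2 days around each.

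The assessment sections write this visit as one time point. For grading: "Investigator will perform clinical grading at the surgical site on each subject at baseline (pre- and post-procedure), day 7/14, and day 28". For symptoms: "Tolerability assessments will be performed by subjects at the surgical site at baseline (pre- and post-procedure), day 7/14, and day 28". Section 10.4 does the same for the questionnaire, and Appendix II has a single form for the visit.

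Section 11 does not mention the two groups. On change scores it says "Mean of the change from baseline (pre-procedure) will be estimated at applicable post-baseline time point". The share improved or worsened is divided by the "total number of subjects". Questionnaire percentages "will be reported for each question and each timepoint". For tolerability, the analysis table adds a rule of interpretation: "A decrease in scores or lack of significant increase indicates tolerability/safety of the treatment product". That rule is not limited to any visit. It covers burning, itching and pain only, not the four clinical grading parameters or the questionnaire.

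**The concern.** Visit 3 is the only assessment between Day 0 and Day 28. If its results are pooled, anatomical site and time since surgery are completely confounded: every head/neck value is about one week old and every body value about two. The pooled mean change, share worsened or questionnaire percentage then belongs to no single post-operative time. Because Section 11 leaves the display open, two analysts could follow it and produce different Visit 3 tables, and the choice could be made after the data are seen.

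The tolerability rule is a second, distinct weakness. It turns a non-significant test in 10 to 20 subjects into a safety conclusion. If the groups behave differently, a pooled test can also fail to show a rise in one of them.

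**Working it through.** **Timing.** 7 ± 2 gives Days 5–9; 14 ± 2 gives Days 12–16. The windows do not overlap.

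**What a pooled figure is.** With 10 + 10 subjects the pooled mean is (m₁ + m₂)/2, which equals either group's mean only if m₁ = m₂. For proportions, an assumed 6/10 worsened in head/neck and 1/10 in body would be reported as 7/20 = 35%, against 60% and 10%.

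**Inputs for the tolerability illustration.** From the documents: n = 10 per group, the 0–3 scale (Section 10.2), and a paired t-test, two-sided at 0.05 (Section 11). The documents give no SD, effect size or power figure, so there is nothing to reproduce. Assumed: head/neck mean change +0.75, with SD 0.6, 0.75 or 0.9; body changes as shown below. The Wilcoxon fallback was not computed for these scenarios.

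**Formulas.** One group: t = m/(s/√10), 9 df. Pooled: S = √{[9s₁² + 9s₂² + 20((m₁ − m₂)/2)²]/19} and t = [(m₁ + m₂)/2]/(S/√20), 19 df.

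**Worked case, SD 0.75.**
- Head/neck alone: t = 0.75/(0.75/√10) = 3.162, p = 0.012, 95% CI 0.21 to 1.29.
- Body −0.25, SD 0.75: S = √[(10.125 + 5)/19] = 0.892; t = 0.25/0.1995 = 1.253; p = 0.225, 95% CI −0.17 to 0.67.
- Body 0, SD 0.75: S = √[(10.125 + 2.8125)/19] = 0.825; t = 0.375/0.1845 = 2.032; p = 0.056.
- Body 0, every subject unchanged: S = √[(5.0625 + 2.8125)/19] = 0.644; t = 0.375/0.1440 = 2.605; p = 0.017.

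| Head/neck SD | Head/neck alone | Pooled: body −0.25, same SD | Pooled: body 0, same SD | Pooled: all body unchanged |
|---|---|---|---|---|
| 0.60 | p=0.003 | 0.167 | 0.027 | 0.008 |
| 0.75 | p=0.012 | 0.225 | 0.056 | 0.017 |
| 0.90 | p=0.027 | 0.285 | 0.096 | 0.033 |

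**Chance of a significant increase** (simulated normal changes, head/neck +0.75, SD 0.75): head/neck alone 80%. Pooled: 17% with body −0.25, 47% with body 0 and 77% with body +0.25 (all body SD 0.75), and 79% with every body subject unchanged.

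**The non-significance rule on its own.** Suppose the observed change is +0.5 with SD 0.75 in both groups. Each group alone gives t = 0.5/0.2372 = 2.108, p = 0.064. Pooled, S = √(10.125/19) = 0.730, t = 3.063, p = 0.006. If +0.5 is the true change, it reaches significance 47% of the time at n = 10 and 81% at n = 20, so the rule would declare tolerability in about 53% and 19% of such trials. The increase detectable with 80% power is about 1.00 SD at n = 10 and 0.66 SD at n = 20.

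**Precision.** The 95% CI half-width is t₀.₉₇₅/√n in SD units: 2.262/√10 = 0.72 and 2.093/√20 = 0.47.

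**The case against.** A reader might infer that the plan pools Visit 3. The documents do not say so. *Applicable* time points can mean separate Day 7 and Day 14 tables, the slash notation can be visit shorthand, and the denominator can be a generic formula. That stands: the defect is an unresolved choice, not a stated pooling rule.

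A reader might also infer that the Day 7/Day 14 mismatch itself hides a safety signal. It does not follow. Post-operative day enters none of the formulas; the masking comes from assuming that the groups differ, and the same changes at Day 28 would give the same p-values. It also depends on baseline. Change is measured from before the procedure on a scale with a floor at 0, so body scores can fall, or vary around no change, only if body subjects had symptoms before surgery. The documents give no baseline scores. With every body subject unchanged, pooling costs almost nothing (79% against 80%). If both groups rise alike, pooling detects the rise better. All of this stands and limits the masking claim.

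Finally, Section 12 has the investigator review changes from baseline and report clinically relevant worsening as an adverse event. This protects individual subjects, so it cannot be said that their worsening would go unseen. It does not correct a group-level tolerability statement drawn from a p-value.

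**Conclusion.** The concern holds in two parts.

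First, Section 11 leaves the Visit 3 display undefined for two groups seen in non-overlapping windows. If pooled, the grading, tolerability and questionnaire results describe neither group unless the two coincide. This needs no assumption about SDs or effects. Day 28 has common timing and is free of this problem.

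Second, reading a non-significant increase as tolerability is unsupported at 10 to 20 subjects, at Day 0 post-procedure and Day 28 as much as at Visit 3. Pooling can make it worse, but conditionally: in the examples it hides a head/neck rise only when body scores fall or vary around no change. At SD 0.75, pooled p runs from 0.225 through 0.056 to 0.017 as the body group goes from falling, to varying around zero, to not changing at all. These figures rest on assumed changes and SDs, normality and full groups of 10.

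This should be corrected, but it does not threaten the study as a whole.

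**What to change.** In Section 11:

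1. Report Visit 3 grading, tolerability and questionnaire results in two columns, Day 7 head/neck and Day 14 body, each with its own denominator. For the scores, give mean change with 95% CI. Label any combined Visit 3 figure as mixing Day 7 and Day 14.
2. At all post-baseline time points, delete the absence of a significant increase as evidence of tolerability or safety. Base the conclusion on mean change with 95% CI and the number worsened out of n: by group at Visit 3, and overall with group values shown at Day 0 post-procedure and Day 28.

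Both changes are needed together. Splitting alone, with the rule kept, would make tolerability easier to claim (p = 0.064 per group against 0.006 pooled in the +0.5 example).

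The cost is plan wording, extra table columns and wider by-group intervals (half-width about 0.72 SD against 0.47 SD). No visits or subjects are added.

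### Section 11 measures and tests every clinical-grading change against a score taken before the study wound exists, so the result depends on the pre-surgical lesion as well as on healing

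*Combined protocol and SAP*

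**What the plan says.** Section 11 defines the test as follows: "The null hypothesis, that the mean change from baseline (pre-procedure) is zero, will be tested using methods described in the Statistical Analysis Plan table". Its table prescribes a paired t-test, with the fallback "If normality fails, a Wilcoxon signed-rank test will be used", and interprets the clinical-grading result as "A decrease in scores indicates an improvement". Tests are two-sided at 0.05.

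The two derived measures share that reference. Percent mean change has "postprocedure or visit mean score" as the first term of its numerator and divides by the pre-procedure mean. The responder percentage counts the "number of subjects improved/worsened from baseline preprocedure"; no threshold for either category is stated. Raw scores are also to be summarised, with "standard deviations, minimum, and maximum of values at all applicable time points".

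Section 10.1 grades erythema, edema and overall wound appearance from 0 to 3 and scabbing/crusting from 0 to 4. For the first three, "half-point scores can be used as necessary to better describe the condition". Score 0 for overall wound appearance reads "Excellent (absent of wound)".

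Section 9.1.2 sets the order on Day 0: grading before surgery (step 2), surgery (step 3), grading again (step 4), first application of the ointment (step 5). The hypothesis in Section 5.2 concerns healing of the wound that surgery leaves.

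**The concern.** The reference grade describes a site on which the study wound has not yet been made. Three things follow.

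- **Floor.** Zero is the lowest score, so a site graded 0 before surgery cannot improve. Complete healing counts as no change. With no threshold stated, any residual score above 0 counts as worsened. If an unoperated site is graded 0 for overall wound appearance, that parameter can only stay the same or get worse.
- **Mixing.** Subjects enter with a lesion that needs a procedure (Section 6.3), and no minimum or maximum pre-procedure score is set. Where that score is above 0 and the procedure takes the lesion away, a later decrease combines its removal with healing of the wound.
- **Timing.** The formula treats the post-procedure grade as an outcome, but it is taken before any ointment is applied. Post-procedure minus pre-procedure reflects surgery only.

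This is the only test planned for clinical grading. It asks whether the site differs from its state before the wound existed, while the hypothesis asks whether the wound heals. A mostly healed panel could be reported as significantly worse. For erythema, edema or scabbing, the same Day 28 scores could be reported as worse, unchanged or better.

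**Working it through.** The plan gives no effect size, standard deviation or power calculation, so there is no figure of its own to reproduce. From the documents I take n = 20 (the maximum number of completers, Section 6.1), the scales in Section 10.1, and the formulas and tests in Section 11. **All scores below are assumed.**

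**Which test applies.** Section 11 names no normality check. In each case in steps 1 and 3, a Shapiro-Wilk test at 0.05 rejects normality, so the Wilcoxon signed-rank test applies. I use its exact form, with zero changes dropped. If all m non-zero changes have the same sign, the two-sided p is 2 × (1/2)^m.

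**1. Same Day 28 scores, different pre-procedure scores.** Day 28 is fixed at ten sites at 0 and ten at 1 (mean 0.5).

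| Pre-procedure score, all 20 | Mean change | Non-zero changes | Exact p | Improved | Worsened |
|---|---|---|---|---|---|
| 0 | 0.5 - 0 = +0.50 | 10 up | 2/1024 = 0.002 | 0% | 50% |
| 0.5 | 0.5 - 0.5 = 0.00 | 10 up, 10 down, equal size | 1.0 | 50% | 50% |
| 1 | 0.5 - 1 = -0.50 | 10 down | 2/1024 = 0.002 | 50% | 0% |

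The second and third rows do not apply to overall wound appearance if an unoperated site scores 0. The second row also excludes scabbing, which has no half-points.

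**2. How little residual is needed when all pre-procedure scores are 0.** Five sites above 0 give p = 2/32 = 0.0625; six give 2/64 = 0.031. Six sites at 1 have a mean change of 6/20 = +0.30. Six at only 0.5, with the other 14 fully healed, have a mean change of 3/20 = +0.15 on a 0-3 scale and the same p of 0.031.

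**3. Mixed pre-procedure scores** (ten at 0, six at 0.5, four at 1; mean (3 + 4)/20 = 0.35).

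- All sites healed at Day 28: change -0.35, ten non-zero changes all down, p = 0.002. This decrease is simply the pre-procedure lesion score.
- Ten residual sites at 1: change 0.5 - 0.35 = +0.15. There are 35 ways to spread them over the three pre-procedure groups. The p-value runs from 0.031 to 0.585 and percent improved from 0% to 50%. Only one of the 35 is below 0.05 (every site with a pre-procedure score above 0 keeps a residual, and every site at 0 heals). The next smallest p is 0.109.

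**4. Ceiling on percent improved.** If k of 20 sites score 0 before surgery, percent improved cannot exceed (20 - k)/20: 75% for k = 5, 50% for k = 10, 0% for k = 20.

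**5. Percent mean change.** It is undefined when the pre-procedure mean is 0. If one subject scores 0.5 and 19 score 0, the mean is 0.5/20 = 0.025. A Day 28 mean of 0.5 is then reported as (0.5 - 0.025)/0.025 × 100 = +1900%.

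**6. The same Day 28 scores measured from the post-procedure grade.** With SD 0.513, the 95% half-width is 2.093 × 0.513/√20 = 0.24.

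| Post-procedure score, all 20 | Mean change (95% CI) | Improved |
|---|---|---|
| 3 | -2.50 (-2.74 to -2.26) | 100% |
| 2 | -1.50 (-1.74 to -1.26) | 100% |
| 1.5 | -1.00 (-1.24 to -0.76) | 100% |
| 1 | -0.50 (-0.74 to -0.26) | 50% |
| 0.5 | 0.00 (-0.24 to 0.24) | 50% |

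The pre-procedure lesion score no longer enters. The new reference is informative only where the fresh wound scores well above 0.

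**The case against.** The strongest case against is about weight, since the reading of Section 11 is not in dispute.

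- **The scores are assumed, and the starkest cases give all 20 subjects the same pre-procedure score**, although Sections 6.1 and 6.2 plan a mix of procedures and body regions. This stands as a limit on size. In the mixed case with residual scores, a significant worsening is a corner result, 1 allocation in 35. The floor, the undefined ratio and the dependence on the lesion score do not need those assumptions.
- **Post-procedure means will be shown descriptively**, so a reader with complete data can subtract. True, but no paired change with its standard deviation or interval, no test and no responder rate is planned from that point.
- **A pre-procedure comparison is a legitimate question about return to the pre-surgical state.** Agreed, but Section 11 does not read it that way: it calls a decrease improvement, so full return from 0 earns no credit.
- **A biopsy need not remove the lesion.** Correct. The mixing of lesion removal with healing applies only where the procedure does remove it.
- **A fall from the post-procedure grade is nearly certain without a control, so its p-value says little.** This also stands. The gain is an estimate that describes the wound; it is no evidence for the product.

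**Conclusion.** The point holds: Section 11 is wrong as written for clinical grading and should be corrected before the analysis. The only planned test of these scores uses a reference that precedes the wound, so its sign and significance depend on the pre-procedure lesion score as well as on healing.

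Confidence is high on the structure. The practical size is not known, because the documents contain no pre-procedure scores. Under the assumed scores, one fixed Day 28 result ranges from significantly worse to significantly better. With all pre-procedure scores at 0, six sites of 20 with a half-point residual are enough for a significant worsening. The effect is clearest for overall wound appearance, provided an unoperated site is graded 0. For erythema, edema and scabbing, the direction depends on the lesion.

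**What to change.** Amend Section 11 as follows.

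- For erythema, edema and overall wound appearance, make the Day 0 post-procedure grade the reference at Visit 3 and Day 28. Use it for the paired change with confidence interval, its test, percent mean change and percent improved/worsened. Interpret the result as an estimate of wound change.
- Keep the pre-procedure contrast as a descriptive return-to-baseline measure, and remove the reading of a decrease as improvement from it.
- State the thresholds for improved and worsened.
- Do not present post-procedure minus pre-procedure as evidence about the product.
- Report scabbing/crusting, which may be near 0 on a fresh wound, as score distributions by visit. Add distributions for erythema and edema, because the documents do not show that these peak immediately after surgery.
- State that, without a control, the change includes natural healing, so a significant fall is expected and does not attribute healing to the ointment.

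The cost is a protocol amendment with IRB approval (Section 14.4). The post-procedure grades are already scheduled, so no visit or measurement is added.
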